6.0 Study Design and Procedures

General Overview

Subjects will attend 1 tDCS tolerability test and training visit, 7-10 testing sessions (2-3 at T0, 2-3 at T1, 2-3 at T2, and 1 follow-up at T3) and 72 remotely supervised tDCS sessions. Testing sessions at four timepoints will involve two to three visits (depending on availability and capacity of the participant). Visit 1: obtain informed consent and administer a pregnancy test, complete the Medical Screening Questionnaire and the TMS and tDCS Safety Questionnaire, measure blood pressure, and perform clinical assessments (1-2 hours). Visit 2: Upper and lower motor neuron mechanisms will be assessed using single-pulse transcranial magnetic stimulation (TMS).

Visit 3: tDCS tolerability testing (30 minutes) will be performed and subjects will be asked to return to the lab with their caregivers for a training session on the use of the Soterix tDCS Mini-CT device (1.5 - 2 hours.). The visits maybe combined if the patient wishes to reduce their travel time. Remotely supervised tDCS sessions are expected to last for 45 minutes which will include up to 20 minutes of stimulation with RS-tDCS and an additional 25 minutes for setting up video conferencing and RS-tDCS equipment. The follow-up testing session will be combined into one visit (up to 4 hours) consisting of the same outcome measures recorded at T0, T1, and T2. If subjects are in the delayed start group, they will receive 24 sessions of sham stimulation followed by 24 sessions of anodal tDCS.

Study Design: Participants will be randomized to receive either sham RS-tDCS (delayed-start control) or facilitatory anodal RS-tDCS (intervention). The intervention group will receive 24 weeks of anodal tDCS (3 times/week; 72 sessions). The delayed-start group will first receive sham tDCS for 12 weeks followed by a switch to anodal tDCS for 12 weeks. Outcome measures will be administered at four time points at entry (T0), at the end of 12 weeks (T1), at the end of 24 weeks (T2) and at a 3-month follow up (T3).

Randomization: Stratified treatment assignment of participants into the two groups will be based on baseline ALFSRS-R score and the pre-slope. Group assignment will be randomized within each category using sequential randomization to achieve study arm balance. Participants and assessors will be masked to the type of stimulation they receive.

Subjects will report to the Brain Plasticity Lab at UIC located at [name]. All subjects will sign a written informed consent. Females of childbearing age will undergo a urine pregnancy test. Subjects who test positive will not be eligible to participate. Female participants of childbearing age will also be informed that the effects of tDCS on pregnancy are still unknown. If participants of childbearing age are planning to get pregnant or may be pregnant during the 24-week period, they will be instructed to stop the tDCS immediately and will be excluded from the study. All subjects will be asked to complete a medical screening questionnaire and TMS and tDCS safety questionnaires. The medical screening questionnaire will include questions about age, gender, race, medical history, medications and personal habits (such as smoking). The TMS and tDCS safety questionnaire will include questions pertaining to the TMS and tDCS exclusion criteria. Blood pressure will be measured prior to conducting clinical assessments. The first testing visit will last for 1 – 2 hours.

Clinical assessments

Clinical testing will take approximately 60 minutes to complete. The battery of functional measures are listed below, and will include tests of walking and balance. The tests have been validated and are commonly used, non-invasive clinical measures.

- Revised ALS Functional Rating Scale (Change in Revised ALS Functioning Rating Scale (ALSFRS-R). Scores range from 0 to 48, with higher scores indicating more function retained.
91. This will be conducted every two weeks over the phone or Zoom PHI.
- Gait speed will be measured using the average speed over two trials of the 10MWT. Change in Revised ALS Functioning Rating Scale (ALSFRS-R). Scores range from

0 to 48, with higher scores indicating more function retained.

Self-selected and fast walking will be measured as the average walking speed from 2 trials of the 10-m walk test, a reliable and sensitive marker for function in patients with ALS.

- 10-meter walk: The 10-meter walk test (10MWT) is a performance measure used to assess walking speed in meters per second over a short distance. It can be employed to determine functional mobility, gait and vestibular function. We will also employ the use of APDM wearable sensors during the test to assess outcome measures of functional mobility.
- Ankle motor control will be assessed using a sinusoidal tracking task. A custom-built ankle-tracking device will be used to quantify the participant's ability to track a computer-generated sinusoidal target with ankle movement
- Other measures: We will examine patient perspective on health outcomes using the Health Related Quality of Life scale, EuroQual-Visual Analog Scale and fatigue using the Fatigue Severity Scale (FSS), 9-item measure from 1 to 7, higher scores = more severe fatigue.

Safety and Feasibility: The number of adverse events (AE) will be actively monitored using structured questionnaires that enquire for AEs related to tDCS during training and lab visits. Key AEs of interest will include 12 symptoms including clinical seizures, skin injury and neurological deterioration (tDCS adverse event questionnaire). The safety of each participant will be assessed on an individual basis throughout his or her involvement with the study. Recruitment and randomization will be assessed using frequency approached for screening and enrollment. Retention will be assessed using proportion of participants enrolled after screening eligibility and number who completed the study. We will collect reasons for study refusals and withdrawals. Acceptability of treatment will be examined using semi-structured patient, caregiver and clinician feedback questionnaires regarding perceived satisfaction, perceived ease-of-use, strengths and weaknesses

Transcranial magnetic stimulation (TMS) and peripheral nerve stimulation (PNS) testing visit

TMS procedures

The TMS procedure will be conducted in the UIC Brain Plasticity Lab. This is the same TMS procedure that has been successfully used in our other research studies (e.g., IRB #2015-0764, #2011-0676, # 2015-1127, # 2011-0284). TMS is a safe, non-invasive method of brain stimulation that has been widely used to study the physiology of the representations of muscles in the motor cortex in healthy and neurologically disordered individuals (Anand & Hotson, 2002). Very short duration (< 1 ms) magnetic pulses are applied via an insulated wire coil placed on the intact scalp overlaying the motor cortical area projecting to a target muscle. Each pulse induces a motor evoked potential (MEP) in a target muscle that can be readily monitored by recording EMG from that muscle. A figure-of-eight or double cone coil is typically used to deliver focal magnetic pulses to a number of scalp sites over the cortical area representing a muscle of interest. Self-adhesive disposable electrodes (Suretrace) with an inter-electrode distance of 2 cm will be applied over the muscle bellies of the tibialis anterior (TA) in the lower

extremity. A ground electrode will be applied over a proximal bony prominence. Standard skin preparation techniques (light abrasion and cleansing with alcohol) will be completed prior to application of the electrodes. EMG recordings will be amplified (Delsys Bagnoli system), band-pass filtered (10-1000 Hz), and sampled at 5000 Hz.

Subjects will be seated, and magnetic stimuli will be delivered via a figure of eight or double cone coils connected to a Magstim 200 unit (Magstim Company, Boston MA). Resting motor threshold for the muscle of interest will be defined as the stimulator output intensity that can elicit a MEP with peak-to-peak amplitude of at least 0.075 mV in four out of eight trials. It will be determined by increasing stimulus intensity in steps of 1% stimulator output. Active thresholds will be determined with the same protocol and defined by the lowest stimulus intensity required to elicit a MEP with a peak-to-peak amplitude of at least 0.1 mV in four out of eight trials with the subject contracting the muscle of interest to about 10% of maximum voluntary contraction. TMS measurements will involve generating MEPs for each muscle. Short intracortical inhibition (SICI) was measured at an interstimulus interval of 2.5 ms. A subthreshold pulse (80% active threshold) was set as the conditioning stimulus and a suprathreshold pulse was set (130% active threshold) as the testing stimulus. To assess corticospinal excitability of the M1, the figure of eight or double cone coil will be placed over the M1 cortical area (near the vertex of the head) and the subject will then receive 15 - 30 stimuli at intensities corresponding to 80% to 130% of rest and active threshold. These measures will assist the investigators to assess the contribution of the motor cortex to the upper and lower limb muscles. The entire procedure should take about 2 hours.

PNS procedures

The PNS procedure will be conducted in the UIC Brain Plasticity Lab under the supervision of [name]. Peripheral nerve stimulation (PNS) will be used to assess lower motor neuron integrity.

Very short duration (1ms) electric pulse is applied to the skin overlying the peripheral nerve that projects to a target muscle. Each pulse induces two evoked potentials in a target muscle that can be readily monitored by recording EMG from that muscle. The first evoked potential is the M-wave and the second is referred to as the H-reflex. The M wave arises from direct stimulation of the motor nerve serving the muscle and its amplitude is used as an estimate of the stimulus intensity delivered to the sensory nerve whose excitation generates the H-reflex. The maximum amplitude M wave that can be obtained in an individual is referred to as the M max, and the stimulus intensities used expressed as a percentage of that needed to produce M max.

Stimulating electrodes will be placed on the lower limb on the skin over the fibular head, longitudinal to the estimated path of the common peroneal or tibial nerve. For upper limb stimulation, stimulating electrodes will be placed on the skin 2cm above the elbow on the lateral part of arm, longitudinal to the estimated path of the radial nerve or on the skin above the wrist joint, longitudinal to the estimated path of the ulnar nerve.

Peripheral nerve stimulation (PNS) will be used to assess lower motor neuron integrity. Similar to TMS, Peripheral nerve stimulation (PNS) will be used to assess lower motor neuron

integrity.

The resting and active threshold for eliciting H-reflexes will be determined for each muscle.

H-reflexes will be evoked using a 1-ms square wave pulse, via a Cadwell Sierra Summit EMG/NCV/EP machine (Cadwell Laboratories, Inc., Kennewick, WA). As outlined in the TMS procedure above, resting motor threshold for the muscle of interest will be defined as the stimulator output intensity that can elicit H-reflex waveforms with peak-to-peak amplitude of more than 50 μ V in four out of eight trials. Active thresholds will be determined with the same protocol, however with the subject contracting the muscle of interest to about 10% of maximum voluntary contraction. The magnitude of the M wave, which arises from direct stimulation of the motoneuron axons serving the autogenic muscle, will be used as an estimate of the stimulus intensity delivered to the large diameter afferent fibers.

The subjects will receive 6 stimulations at each of 7 intensities ranging from 70% of H-reflex active threshold to 110% M max.

All subjects will report to the lab for a tDCS tolerability test. Lab personnel will test the subject's tolerability to stimulation with tDCS. tDCS electrodes will be placed on the subject's scalp and stimulation will be performed for 20 minutes. Subjects will be assessed for side effects. Subjects will also complete a RS-tDCS training session which will last for 1.5 – 2 hours.

Device information and training of study personnel

A portable tDCS device (Soterix Medical 1X1 tDCS mini-CT Stimulator) will be issued to the subject upon completion of training. All subjects will be directly trained by research personnel. Research personnel will be trained by the device manufacturer (Soterix Inc.) in the preparation and testing of the tDCS device and electrodes prior to providing it to participants, as well as appropriate documentation of the device release. This device has built in programmable codes which allows for strict dosage control which can be monitored remotely. The device would be deactivated until a code is provided by the research staff to the subject for every session. The code unlocks a single session with a pre-set duration and intensity that would be pre-programmed. After a single discharge, the device is inert until a new code is provided. This allows the remote supervisor to control tDCS application, as the code may not be provided until the researcher is satisfied with the placement of the electrodes via video conference. The subject or caregiver cannot change stimulation intensity or treatment duration which enhances safety and reproducibility.

Study staff will be familiarized on the usage of the device and the location of headset placement. In addition, selected research staff (who are not blinded to the study) will be trained with and have access to the device manual that enlists in a step-by-step fashion, the procedures that are required to program the device prior to release to subjects, for example programming device unlock codes for one-time use to be provided prior to each session. Prior to releasing a device to a subject, study staff will program the intensity, duration, and condition of each planned session, along with a code that limits the number and frequency of sessions. This will be double checked by the Principal Investigator prior to release of the device to the subject. Through the duration of the study, study staff will be trained to monitor subjects for any unexpected adverse events (e.g., atypical discomfort) or misuse of the device. At the end of the study, study staff will evaluate retrieved device materials (e.g., headgear/stimulator condition, gel) and download any data stored on the device (e.g. completion codes for each subject's study sessions, stimulation history of each code issued) as relevant to confirm compliance.

Training of subject/ caregiver:

At the training visit, study personnel will complete a tDCS checklist (Supplement _tDCS checklist) to screen subjects for at home RS-tDCS. In the training session, the participant and caregiver will be familiarized to the device, electrode positioning and placement on the scalp. The subject/caregiver will be trained to properly apply the headset and correctly operate the device.

At the training visit, subjects will be measured for individually fitted and engineered headband locators for electrode placement. Headbands are measured and marked relative to ear tragi, the

nose and midline of scalp. A separate occipital band ensures the locator headband cannot slip from its position. The headgear will allow consistent placement of electrode at the lower limb motor cortex area on the scalp (1 cm posterior and 1 cm lateral to the vertex, Cz). The headgear will be marked with “RED” and “BLACK” to confirm that color coded leads are properly placed, ensuring Anode (Red) and Cathode (Black) and the subject is shown how the electrodes are placed (see figure). Once fitted, subjects are shown how to position the headbands reproducibly and instructed on how to position the band markers relative to the anatomical landmarks described. The subject/caregiver will then demonstrate tDCS application and electrode placement under the supervision of the researcher. The research personnel will use a checklist to identify if the participant/caregiver has understood device operating instructions.

Photographs and measurements will be taken in case the subject needs for reference at home and all instructions are given in an information guide as well. The investigators will then confirm that the subject and caregiver /partner have understood all details of the stimulation. We will provide study training materials i.e. an information guide (Supplement_Information guide and Stimulation Manual), a RS-tDCS session log [to record the number of treatment sessions] (Supplement_tDCS session log), and RS-tDCS equipment (headgear and 12 electrode sets) along with other supplies for the entire study. We will also provide a RS-tDCS side effects survey (Supplement_tDCS side effects survey) in which subjects are informed of potential side effects such as tingling, burning sensation, dizziness, headache, nausea and phosphenes while switching the device on or off abruptly. Subjects will also be provided a RS-tDCS ease of use form (Supplement_tDCS ease of use) for reporting their experience of equipment use, including convenience.

Following the training visit, the subject would be provided a schedule for RS-tDCS sessions (monitored via Zoom PHI). The researcher will remotely observe the placement of the electrodes and the headset and supervise each of the 72 sessions. The subject will also be asked to report adverse effects at the beginning and end of every session. Participants will be instructed to contact the Emergency Department in the event of experiencing serious side effects.

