4.0 Eligibility

4.1 Inclusion Criteria

The general inclusion criteria will be approximately 100 males and females of any race or ethnic status with the following characteristics:

- Age between 18 – 80 years
- Diagnosis of possible, probable, or definite amyotrophic lateral sclerosis according to El Escorial revised criteria
- Spinal onset ALS with initial weakness in the upper or lower extremity.
- Diagnosed with ALS within the past 5 years
- 1-2 point change in pre-slope of the ALSFRS-R at time of enrollment (ratio of drop in score from 48 to the duration in months from onset of weakness)
- Score ≥ 2 for “swallowing” of the ALSFRS-R
- Score ≥ 2 for “walking” of the ALSFRS-R
- Able to provide informed consent
- Stable dose of riluzole, edaravone, AMX0035 (Relyvrio) or no medications
- Availability of a caregiver for remote administration of tDCS

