9.0 Data Analysis

We will look at pre and post changes in our primary and secondary outcomes measures. A one-way ANOVA will be used to examine changes in adverse events, subject dropouts, and TMS and clinical assessments. A two-way repeated measures ANOVA with groups and time as the two factors will be used to analyze change scores on adverse events, TMS and clinical assessments.

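### Limb of onset is missing from both the strata and the model, although stimulation and the performance tests are leg-specific; adding it, with a leg-item ALSFRS-R analysis, is a nearly free gain in precision and interpretability

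*Combined protocol and SAP*

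**What the plan says.** **Stimulation site.** Section 6.0 (training of subject and caregiver) gives one site for all participants: "The headgear will allow consistent placement of electrode at the lower limb motor cortex area on the scalp". No arm-area placement is described.

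**Population.** Section 4.1 requires "Spinal onset ALS with initial weakness in the upper or lower extremity", so both onset types enter. It also sets a floor on leg function for everyone: "Score ≥ 2 for “walking” of the ALSFRS-R".

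**Outcomes.** The performance tests in Section 6.0 are leg tests: "Self-selected and fast walking will be measured as the average walking speed from 2 trials of the 10-m walk test" and "Ankle motor control will be assessed using a sinusoidal tracking task". For TMS, tibialis anterior is the only muscle named for EMG electrodes. The same section nevertheless says that the TMS measures cover both upper and lower limb muscles, and its peripheral nerve procedures give arm sites (radial or ulnar nerve). Aim 2 uses the ALSFRS-R, scored 0 to 48, which Section 3.0 lists among secondary outcomes. No leg subscore is defined.

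**Randomisation.** "Stratified treatment assignment of participants into the two groups will be based on baseline ALFSRS-R score and the pre-slope".

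**Analysis.** Section 9.0: "A two-way repeated measures ANOVA with groups and time as the two factors will be used to analyze change scores". No covariate, onset term or subgroup appears.

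**Sample size.** Section 12.0 plans 50 per group and justifies this on adverse events.

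**The concern.** Limb of onset is a plausible predictor of how fast leg measures decline. The two stratification factors describe overall severity and overall rate of loss, not the region affected: two patients with the same total and the same pre-slope can differ in how far the legs are involved. Leaving onset out of the model puts explainable variance in gait speed, ankle tracking and tibialis anterior responses into the error term.

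The second matter is interpretation. The stimulated region is the leg area, while Aim 2 is read on a whole-body total. If the total shows nothing, the planned analyses cannot separate no effect from a regional effect that was diluted. Section 12.0 says the study should inform a future trial, and the choice of population and endpoint for that trial is where this information would be needed.

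**Working it through.** The plan gives no figure on this point to reproduce. What follows is illustrative and rests on stated assumptions.

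**Inputs.** From the documents: 50 per group (Section 12.0). Assumed: half have upper-limb onset; the onset groups differ by d = 0.3 to 0.8 SD in change on a leg outcome (SD within onset group); one comparison at one visit; no dropout.

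**1. Chance imbalance.** Taking the two groups as independent Binomial(50, 0.5) counts, a difference of 5 or more patients (10 points) has probability 0.37, and 8 or more (16 points) 0.13. With the overall split fixed at 50/50 and allocation hypergeometric, the figures are 0.32 and 0.16.

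**2. Shift in the estimate.** Shift = imbalance × d, for a 16-point imbalance:
- d = 0.3: 0.16 × 0.3 = 0.05 SD
- d = 0.5: 0.16 × 0.5 = 0.08 SD
- d = 0.8: 0.16 × 0.8 = 0.13 SD

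**3. Standard error.** Adjusted: √(2/50) = 0.20 SD. Unadjusted: √[(2/50)(1 + 0.25d²)], where 0.25 = 0.5 × 0.5 is the variance of a half-and-half onset indicator.
- d = 0.3: √(0.04 × 1.0225) = 0.202; adjustment cuts it by 1 − 1/√1.0225 = 1%
- d = 0.5: √(0.04 × 1.0625) = 0.206; cut 3%
- d = 0.8: √(0.04 × 1.16) = 0.215; cut 7%

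The shift in step 2 must be compared with the unadjusted standard error, because that already includes the chance imbalance. At d = 0.8 this is 0.13 against 0.215 SD.

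**4. Dilution in the total.** Suppose the score has m equal-variance items with common correlation ρ, and an effect falls equally on k of them. The standardised effect on the k items, relative to the total, is √{m[1 + (m − 1)ρ] / (k[1 + (k − 1)ρ])}. The documents give only the 0-48 range and name two items (swallowing and walking), so m, k and ρ are all assumptions.
- m = 12, k = 3, ρ = 0: √(12/3) = 2.0
- m = 12, k = 3, ρ = 0.3: √(51.6/4.8) = 3.3
- m = 12, k = 6, ρ = 0: √(12/6) = 1.4

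The sample-size ratio is the square of each: 4, about 10.8 and 2.

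**5. What results by onset could show.** With 25 patients per group-by-onset cell, the onset-by-group interaction detectable with 80% power at two-sided 0.05 is (1.96 + 0.84) × √(4/25) = 1.12 SD. Anything smaller would usually be missed.

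**The case against.** The strongest reply is that this is a pilot sized on adverse events, that Section 3.0 ranks the ALSFRS-R as secondary, and that a whole-body score is a defensible measure of disease progression. The protocol nowhere hypothesises an effect confined to the legs. The minimum walking score limits baseline differences in leg function, and the existing strata cover part of prognosis. At the lower end of the assumed range, adjustment gains only 1%. All of this stands, and it makes the point a refinement.

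A reader might be tempted to infer more, in four ways that the documents do not support:
- **That the comparison is biased.** Allocation is randomised. Chance imbalance is already part of the unadjusted standard error, so its cost is lost precision and should not be counted a second time as bias.
- **That all TMS and nerve outcomes are leg outcomes.** Section 6.0 also mentions upper-limb muscles and arm nerves. The text leaves open which muscles are analysed.
- **That the trial's efficacy claim as a whole rests on the total.** This is true of Aim 2 only.
- **That the dilution has a known size.** The item breakdown is not in the documents.

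Whether the stimulation site or the eligibility rule suits patients with arm onset is a clinical question, on which no view is taken here.

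**Conclusion.** The point holds as a modest one about precision and interpretability. The validity of the comparison is not in question. The facts it needs are in the text: one leg-area site, both onset types admitted, leg-only performance tests, and limb of onset absent from strata and model. The precision gain is about 1% to 7% of the standard error on leg outcomes, if the onset groups differ by 0.3 to 0.8 SD and are about equal in number. Dilution of a leg-confined effect in the ALSFRS-R total could be larger than that, but it is conditional on such an effect existing and on assumed item numbers and correlations. Results by onset can only be exploratory at this sample size.

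**What to change.** 1. Keep the ALSFRS-R total for Aim 2.
2. Record limb of onset (upper or lower) as a data field. Screening has to establish that onset was in a limb, but the protocol does not say that which limb is captured for analysis.
3. In Section 9.0, add limb of onset as a baseline covariate, with an onset-by-time term in the repeated-measures models, for ALSFRS-R, gait speed, ankle tracking and tibialis anterior TMS.
4. Pre-specify the leg-related ALSFRS-R items, listed by name and including walking, as a supportive outcome.
5. Report results by limb of onset, labelled exploratory.
6. State in Section 6.0 which muscles and nerves are tested and analysed.

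The strata can stay as they are, since the covariate recovers the precision described above. The cost is one or a few degrees of freedom per model: with change scores at T1, T2 and T3, one for onset and two for onset by time. One data field is added, and visits, eligibility and stimulation do not change. The additions should be written down before any unblinded comparison, including the planned interim look after six participants.
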